Outcome Measures	To develop a new mHealth smartphone application to engage primary caregivers directly in the active monitoring of their infants' development, and to provide tailored feedback and support for the provision of nurturing care.	To collect data on usability and acceptability of the technology to end users and determine effect size of clinical effectiveness (infant development outcomes). The primary outcome is BSID-4 as a measure of infant developmental outcomes.	To test clinical effectiveness (improved infant development outcomes and caregiving behaviors). The primary outcome is BSID-4 as a measure of infant developmental outcomes. The secondary outcomes are quality of infant-caregiver interaction (NCAST feeding scale) and quality of the home environment (HOME scale).	

- In Aim 1, we will develop a new mHealth smartphone application which can be used to engage primary caregivers directly in the active monitoring of their infants' development, and to provide tailored feedback and support for the provision of nurturing care. Aim 1 will use focus groups, an Agile Design process, and the RE-AIM framework for assessment.
- In Aim 2, we will prospectively assess the implementation characteristics of the technology—usability, acceptability, and sustainability—for caregivers over time for different periods of infant development. Aim 2 will use a prospective, longitudinal, six-month pilot intervention, enrolling 40 caregivers and their infants from birth to 4 weeks of age (using simple randomization to assign them to either the 6-month smartphone intervention (n=20) or control (receipt of printed parenting materials, n=20).
- Aim 3 is similar to Aim 2 only 1) it is adequately powered based on Aim 2 results with 110 participants per group, 2) the developmental outcome (BSID-4) will be measured at 18 months in Aim 3 instead of 6 months in Aim 2, and 3) we will add assessment of quality of infant-caregiver interaction as measured by the Nursing Child Assessment Satellite Training (NCAST) feeding scale and Home Observation for the Measurement of the Environment (HOME scale).

BACKGROUND AND SIGNIFICANCE:

(Brief paragraph summarizing any information important for understanding the study and proposed research procedures)

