Aim 2 Study Design. Two-arm prospective, longitudinal, randomized 6-month pilot intervention. We will assess the implementation characteristics of the smartphone application through a longitudinal, six-month usability trial, to determine caregiver engagement over time and to assess the perceived usefulness of the application. Aim 2 will complement the technical work in Aim 1 by conducting a larger-scale pilot implementation of the caregiver smartphone application. Aim 2 is designed to collect data on usability and acceptability of the technology to end users and determine effect size of clinical effectiveness (infant development outcomes).

Aim 3 Study Design. Two-arm prospective, longitudinal, randomized 18-month intervention with developmental outcomes assessed at 18 months. Aim 3 will determine the effectiveness of a smartphone-based, real-time caregiver feedback intervention to promote positive infant developmental outcomes and improved caregiving behaviors. Aim 3 will test clinical effectiveness (improved infant development outcomes and caregiving behaviors).

Eligibility criteria:

Criteria for all aims of the study will be as follows:

Inclusion Criteria: Consenting first-time caregivers with an infant in the eligible age range (0-4 weeks), singleton, full-term (>37 weeks) birth. For stakeholder interviews and application testing phases, any consenting caregiver with an infant less than 6 months of age and a smartphone, or any Maya Health Alliance staff member who works with infants will be eligible to participate.

Exclusion Criteria: Presence of acute malnutrition/wasting or severe medical illness (heart disease, kidney disease, congenital abnormality), medical need for supplementation of breastfeeding, caregiver not literate (our exploratory feasibility data in preparation for this proposal shows that >95% of first time caregivers in the region are now literate).

Recruitment:

The caregivers participating in both phases (Aim 1, design/formative phase; Aim 2, implementation/trial phase) will be recruited from among first-time caregivers receiving services at a major maternal-child wellness clinic run by Maya Health Alliance out of their main office in Tecpán Guatemala.

For Aim 1, up to 20 caregivers will be recruited in this fashion for formative focus groups. Up to 20 Maya Health Alliance staff will be recruited. All staff who work in early child development and nutrition programs will be eligible. Recruitment will be by word of mouth.

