smartphone application. Study staff will make an initial home visit (less than an hour) to install the application on the caregiver phone and demonstrate use and collect baseline data. The baseline data will include: infants/caregivers demographics, poverty scorecard, infant's pre- and post-natal medical history and anthropometrics. The baseline data will be collected using an electronic RedCap form. "Teach back" demonstration will be used to assure understanding. Subsequently, in the intervention arm, staff will make monthly visits (approximately 15 minutes duration) to assess functionality of the smartphone and answer questions/reinforce use. In the control arm, staff will make monthly visits (approximately 15 minutes duration) to ask if there are questions about the printed caregiving materials. The smartphone app in the intervention arm will function as follows. On 3 consecutive days per week it will query caregivers to complete a 20-second survey that asks about 1) frequency, amount and type of feeding, 2) frequency and duration of sleeping, or 3) frequency, duration and type of activity and interaction, subsequently providing reinforcing feedback based on entered data and permitting direct interaction (by phone/text) with health workers from Maya Health Alliance for problem areas identified as described above. On non-survey days, the app will provide age-based anticipatory guidance (Table 2). For the 6-month study, there will be a total of 9 visits. The study will last 6 months and consist of 7 home visits by research staff (initial visit and monthly follow-up visits months 1-6) and 2 BSID-4 assessment visits (at baseline and conclusion). The BSID-4 can be completed in a space provided by the institution or close to where the subject lives to ensure comfort for their child. During the home visits, research staff will also collect the following information from all subjects (intervention and control): Infant/caregiver demographics (first visit), infant's medical history (first visit), caregiver poverty scorecard (first visit), infant's height and weight (each visit). For the intervention arm, app usability (*System Usability Scale Survey*) and usefulness and satisfaction (*Usefulness and Satisfaction Survey*) scales will be done at the first and last visit. These surveys will be collected using an electronic RedCap form. This information will be collected for research purposes only and will be obtained directly from the caregiver. The BSID-4 will be measured at enrollment and study conclusion during a separate assessment visit (less than an hour in duration). A semi-structured interview with subjects enrolled in the intervention group at the last visit will be used to qualitatively assess interest, engagement, and perceptions of the app technology. This interview will be audio-recorded to accurately capture each subjects response. The audio-recordings will not be shared outside the research team and will be destroyed once they have been transcribed.

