
Aim 3: Two-arm prospective, longitudinal, randomized 18-month intervention with developmental outcomes assessed at 18 months. Recruited caregivers/infants will undergo simple randomization to one of 2 arms. The control arm will receive printed caregiving materials based on recommendations outlined in Table 1. The intervention group will receive the smartphone application. Study staff will make an initial home visit (less than an hour) to install the application on the caregiver phone and demonstrate use. "Teach back" demonstration will be used to assure understanding.

Subsequently, in the intervention arm, staff will make visits every 3 months (less than 1 hour duration) to assess functionality of the smartphone and answer questions/reinforce use.

In the control arm, staff will conduct visits every 3 months (less than 1 hour duration) to ask if there are questions about the printed caregiving materials. The smartphone app in the intervention arm will function as described above in Aim 2, including the semi-structured interview. This intervention phase of the study will last 18 months. The NCAST feeding scale and HOME scale will be administered at visits 0, 6 months, 12 months, and 18 months. The BSID-4 will be measured at 18 months (less than an hour in duration). BSID-4 will be completed during separate assessment visits. There will be a total of 8 home visits by research staff (initial visit, 3 month follow-up visits months 1-6 and 1 visit at the end of the study for BSID-4). Also, during the home visits, research staff will also collect the following information: Infant/caregiver demographics, infant's medical history, caregiver poverty scorecard, and infant's measurements and weight. This information will be collected for research purposes only and will be obtained directly from the caregiver.

Primary Outcome:

The primary outcome is BSID-4 as a measure of infant developmental outcomes. It is a standardized assessment of cognitive, motor, and language development. Research staff interact with the child in a standardized way and observe his or her behavior.

Secondary Outcomes:

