4. There is the risk that there will be discordant interest between a caregiver and other family members about wanting to participate in the study which might cause conflict, particular in the case of a single mother or where other extended family members exercise significant decision making power over the primary caregiver

5. Some of the questions may make the participant feel uneasy or embarrassed. However, participants may choose to skip or stop answering questions at any time.

EXPECTED BENEFITS:

(Describe expected benefits to subjects as well as the benefit to society that may result through an increase in knowledge)

Stakeholder participants will benefit mostly indirectly from this project by helping to improve implementation knowledge around mHealth and infant development interventions in Guatemala. However, they may also benefit directly from a greater sense of empowerment and job satisfaction, by participating.

Children and caregivers enrolled in the study may benefit directly from participation. Potential benefits include improvements in developmental and growth outcomes. For caregivers, an enhanced knowledge of early child development and improved self-efficacy as caregivers are other potential benefits. Caregivers' may see improvement in some or all their child's symptoms.

The information gained through this project will contribute important, practical insights into the implementation of mHealth interventions in LMIC, at minimal risk to participants. The results of this project will develop mHealth smartphone technology which can be used to engage primary caregivers directly in the active monitoring of their infants' development, and to provide tailored feedback and support for the provision of nurturing care. In addition to design of the technology, we will also prospectively assess the implementation characteristics of the technology—usability, acceptability, and sustainability—for caregivers in a rural Guatemalan population which is at high risk for impaired infant growth and development. Following successful implementation in Guatemala, this mHealth method could then be expanded to families with at-risk infants worldwide.

EQUITABLE SELECTION OF SUBJECTS:

(No group of persons should be excluded from research, with its associated risks and benefits, without justification. Provide a justification for your selection criteria. Also, explicitly address your plan for overcoming any cultural or language barriers that pertain)

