This was a single-center, individually randomized (1:1 allocation ratio), parallel-group pilot trial to compare use of the smartphone app to printed educational materials. First-time primary caregivers and their infant were eligible to participate if the infant was 0-28 days old at the time of recruitment and a singleton full-term (≥ 37 weeks) birth. Infant exclusion criteria were acute malnutrition (weight-for-length/height Z score ≤ -2 SD using WHO standards), severe medical illness, or medical contraindication to breastfeeding. Caregiver exclusion criteria were inability to read or speak Spanish. Eligible caregivers who did not possess a functioning Android smartphone were given a phone for the duration of the study.

Subjects were recruited by trained research nurses within usual clinical care settings after referral by healthcare providers working at Maya Health Alliance. Verbal consent was obtained following Maya Health Alliance protocol for a minimal-risk study with Indigenous populations as obtaining signatures is not a culturally common practice. Study visits and data collection occurred in the home by trained research nurses, except for the secondary outcome variable (Bayley Scales of Infant Development, Version 4; BSID4; Pearson Assessments, San Antonio, TX, USA) which was collected by consulting psychologists in clinical spaces at Maya Health Alliance.

After enrollment and randomization, caregivers received either the smartphone app, installed with assistance from a study nurse, or printed materials. Brief monthly visits (~ 15 minutes) were conducted monthly for 5 consecutive visits by a study nurse to resolve questions about the app or, in the comparator arm, to resolve any caregiver questions about the printed materials. BSID4 data was collected at enrollment and study exit at 6 months post enrollment.

STATISTICAL ANALYSIS PLAN

Quantitative statistical analysis was conducted using Stata Version 17. Demographic and clinical characteristics of study participants were summarized using means and standard deviations; median and interquartile range; or percentages, as appropriate. For BSID4 outcomes, raw differences between intervention and control arms in composite scores were summarized and adjusted differences calculated using linear regression with adjustments chosen *a priori* for sex of child, caregiver educational level, poverty score, birth weight and change in length for age Z score from 0 to 6 months.

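### The 6-month pilot labels BSID-4 both primary and secondary and names no other primary outcome, and its only adjusted model conditions on growth measured after randomization

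*Combined protocol and SAP*

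**What the plan says.** **Outcome label.** In the Protocol Summary Form, Table 1, the Outcome Measures cell for Aim 2 gives the pilot's purpose as usability, acceptability and to "determine effect size of clinical effectiveness (infant development outcomes). The primary outcome is BSID-4 as a measure of infant developmental outcomes". The Study Protocol (Trial design and participants) says that data were collected at home by research nurses "except for the secondary outcome variable (Bayley Scales of Infant Development, Version 4; BSID4", which psychologists administered in clinic space. No sentence in the Study Protocol or SAP designates a primary outcome.

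**Other candidate measures.** The Form's Aim 2 Study Design says "Aim 2 is designed to collect data on usability and acceptability of the technology to end users", alongside effect size. Study Procedures, Aim 2, schedules two scales for the opening and closing visits: "For the intervention arm, app usability (*System Usability Scale Survey*) and usefulness and satisfaction (*Usefulness and Satisfaction Survey*) scales will be done". An interview with intervention-arm caregivers is also planned, to be assessed qualitatively.

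**Analysis.** Beyond describing participant characteristics, the SAP has one analysis: "For BSID4 outcomes, raw differences between intervention and control arms in composite scores were summarized and adjusted differences calculated using linear regression". The covariates, described as chosen in advance, are infant sex, caregiver education, poverty score, "birth weight and change in length for age Z score from 0 to 6 months". The SAP does not say whether the raw or the adjusted difference is the main one.

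**Growth.** Under Expected Benefits, the Form says of enrolled children and caregivers: "Potential benefits include improvements in developmental and growth outcomes".

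**The concern.** A reader needs to know whether the pilot's BSID-4 difference is its main result or a supportive one. The documents give both answers. On the Study Protocol's answer, the main result is not identified at all, and the only outcome analysis is of a secondary outcome.

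The covariate is a separate matter. Sex, education, poverty score and birth weight are fixed before randomization, so adjusting for them leaves the target of estimation unchanged. Change in length-for-age from 0 to 6 months is not. The app gives feeding guidance, so growth could lie on the path from app to development, or share causes with it. Conditioning on it can then remove or distort part of the effect that the comparison is meant to show. With no hierarchy between raw and adjusted, two estimates that may answer different questions are offered on equal terms.

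**Working it through.** The plan gives no figure to reproduce here: no significance level, power, effect size or SD is stated for the pilot. The first two steps compare texts; the last two are short arithmetic.

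**Step 1. Is it the same trial?**

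| Feature | Form, Aim 2 | Study Protocol |
|---|---|---|
| Design | two-arm randomized pilot | 1:1 randomized parallel-group pilot |
| Comparison | app against printed materials | app against printed materials |
| BSID-4 timing | enrollment and 6 months | enrollment and 6 months |
| BSID-4 status | primary | secondary |
| Other primary named | none | none |

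Aim 3 runs 18 months with 110 per arm and measures BSID-4 at 18 months, so the Study Protocol is not describing Aim 3. Both texts stand in one document dated 8/9/2023, and neither is marked as superseded. The Form's stand-alone Primary Outcome section also names BSID-4 but does not say for which aim. The NCAST and HOME secondary outcomes that follow it belong to Aim 3, so that section does not settle the matter.

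**Step 2. What each reading leaves.**
- BSID4 secondary: there is no named primary outcome and no primary analysis. The two usability and satisfaction scales have no stated analysis either.
- BSID4 primary: the Study Protocol mislabels it. The Form says of the scale: "It is a standardized assessment of cognitive, motor, and language development". No text says which composite leads, or whether raw or adjusted does.

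**Step 3. The growth covariate.** In linear regression, adding one covariate moves the arm coefficient by an exact amount:

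gap = (estimate with baseline covariates only) − (stated model) = δ × β

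Here δ is the between-arm difference in length-for-age change, given the baseline covariates, and β is the coefficient of that change in the stated model. Both are in SD units. β can be non-zero because growth affects development or because the two share causes; either way the gap also needs δ to differ from zero.

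Neither value is in the documents. With assumed δ of 0.2 to 0.5 and assumed β of 0.2 to 0.4:

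| δ | β | gap (SD) |
|---|---|---|
| 0.2 | 0.2 | 0.04 |
| 0.2 | 0.4 | 0.08 |
| 0.5 | 0.2 | 0.10 |
| 0.5 | 0.4 | 0.20 |
| 0 | any | 0 |

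**Step 4. Precision, for context.** The unadjusted 95% half-width for one composite is t(2n−2) × √(2/n) in SD units. With n = 20 per arm it is 2.024 × 0.316 = 0.64. With an assumed 10% or 20% loss (n = 18 or 16) it is 2.032 × 0.333 = 0.68 or 2.042 × 0.354 = 0.72. This follows from the sample size whichever label is right, so it does not measure the defect. It shows only that an interval must accompany each estimate.

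**The case against.** The strongest reply is that little turns on the label. The pilot is written up in the past tense, its SAP states no test, significance level or success rule, and a pilot may properly confine itself to estimation. This stands, and it limits the severity: no confirmatory claim in the text depends on which label is right.

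Second, a reader might infer that usability was the true primary outcome and went unanalysed. The documents do not support that. They give usability and acceptability as purposes of the pilot and schedule two scales, but no passage calls either one primary. The SAP's analysis text is expressly quantitative, so its silence on the interview is not a gap. What remains is that the two numeric scales have no stated analysis.

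Third, a reader might infer that the adjusted estimate is biased, perhaps by as much as 0.20 SD. That is not shown. The Expected Benefits text covers everyone enrolled and claims no difference in growth between arms. The control arm's printed materials rest on the same Table 2 guidance, feeding included. The values of δ and β are assumptions, and the gap may be zero. What stands is that the covariate is measured after randomization and that nothing in the plan excludes an effect on it.

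Fourth, the trial is stated to be prospectively registered, and the registration may settle which outcome was prespecified. That may be so. The finding concerns what these documents say, and they disagree.

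**Conclusion.** The contradiction holds on the text alone: for the same pilot, BSID-4 is primary in Table 1 and secondary in the Study Protocol. If it is secondary, neither a primary outcome nor a primary analysis is given. A reader might go further and infer that the outcome was switched after the fact. Nothing here shows that; the documents show two live, conflicting labels and no more.

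The covariate point also holds, conditionally. If the app changes growth relative to print and growth predicts BSID4, the stated adjusted model does not estimate the app's total effect. The size is unknown; the 0.04 to 0.20 SD range rests wholly on assumed inputs, and zero is possible.

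This should be corrected before the pilot is interpreted, but it does not invalidate a completed pilot that states no test or success rule. Nor can it be carried over to Aim 3: the Form says that 110 per arm rests on Aim 2 results but gives no effect size, SD, significance level or power with which to trace the link.

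**What to change.** 1. Reconcile Table 1 (Aim 2 column) with the Study Protocol, and say which aim the Primary Outcome section covers. State the primary outcome that was prespecified for the pilot, and label any change made now as post hoc.

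2. For each BSID4 composite, report the between-arm difference with a 95% CI. Take as the main estimate a linear model with the stated baseline covariates only: sex, caregiver education, poverty score and birth weight. The enrollment BSID4, already collected, may be added. Show the raw difference and the stated model, with length-for-age change included, beside it. Label the choice of main estimate post hoc.

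3. If usability or acceptability was the intended primary outcome, add a descriptive intervention-arm summary of the two scales with CIs, or say that they were not collected; the Study Protocol does not mention them. The one-arm 95% half-width is t(n−1)/√n: 2.093/4.472 = 0.47 SD with 20 caregivers, or 2.131/4 = 0.53 SD with 16.

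**Cost.** Wording changes in three places, plus about one refit per composite on data already held, so about three if each of the three domains has its own composite. The remaining price is the post hoc label: a hierarchy chosen after data collection cannot carry the weight of a prespecified one. Keeping the stated model in view prevents the refit from looking like a replacement chosen for its result.

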Title: Mobile Health Intervention to Promote Positive Infant Health Outcomes in Guatemala

NCT Number: NCT05106894

Date of Document: 8/9/2023

PI: [name], PT, DPT, PhD, Email: [contact] , Children's Hospital Los Angeles

**Wuqu' Kawoq | Maya Health Alliance (Maya Health Alliance or MHA)
Protocol Summary Form**

NAME OF PRINCIPAL INVESTIGATOR:

[name] (CHLA)
[name] (WK)

PROTOCOL TITLE: Mobile Health to Promote Positive Infant Outcomes in Guatemala

SOURCE OF FUNDING: United States National Institutes of Health

SPECIFIC AIMS:

(State objectives concisely, describe hypothesis tested)

Investments made early in the life course—especially efforts directed at supporting development in the first two years of life—are more cost-effective than interventions later in childhood and can permanently enhance development (5-9). Consequently, one of the most effective and evidence-based interventions for ensuring healthy child development is the promotion of high-quality, nurturing care by primary caregivers in the first months of life (10) (See Table 1).

Table 1

STUDY AIMS			
	Aim 1	Aim 2	Aim 3
Study Design	Prospective single visit or repeated visit small group interviews	Two-arm prospective, longitudinal, randomized, 6-month pilot intervention to assess the implementation characteristics of the technology—usability, acceptability, and sustainability. Outcomes assessed at 6 months.	Two-arm prospective, longitudinal, randomized 18-month intervention with developmental outcomes assessed at 18 months to help determine the effectiveness of a smartphone-based, real-time caregiver feedback intervention.
Study Procedures	Focus groups	The intervention arm (n=20) will receive the smartphone application. The control arm (n=20) will receive printed caregiving materials.	The intervention arm (n=110) will receive the smartphone application. The control arm (n=110) will receive printed caregiving materials.
Recruitment	Up to 20 caregivers and up to 20 Maya Health Alliance staff will be recruited for formative focus groups	40 caregivers and their infants from birth to 4 weeks of age	220 first-time caregivers and their infants from birth to 4 weeks of age

Duration	Focus groups will be 1-2 hours in duration.	6 months with 7 home visits by research staff (initial visit and monthly follow-up visits months 1-6)	18 months with 8 home visits by research staff (initial visit, follow-up visits every 3 months and 1 visit at the end of the study for BSID 4).	

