These participants will then be invited, as they are willing, to participate in the formative agile design phase of the app. Subsequently, in Aims 2 and 3, 40 and 220 (respectively) additional caregiver/infant dyads will be recruited in the same fashion into participate in the prospective implementation trial.

Study Procedures:

Aim 1: **Focus groups:** User perspectives will be collected using a focus group format, facilitated by a research staff at Maya Health Alliance under the supervision of [name], who is fluent in Spanish and Kaqchikel Maya, so that speakers who prefer either language can be included. Convenience samples of caregivers who own smartphones and have infants 0-6 months old will be recruited from Maya Health Alliance clinics, taking care to recruit both male and female caregivers. These will be supplemented by additional focus groups with Maya Health Alliance early child development staff (nurses, technicians, physicians). Four focus groups (1-2 hours in duration) will be conducted, with 5-10 participants each (2 groups caregivers, 2 groups staff). Additional focus groups, up to 5 total, will be held as needed so that preference can be given to those who prefer to conduct the sessions in Spanish or Kaqchikel. During the focus groups, participants will be asked about their opinions around their experience with smartphone applications and understanding of an mHealth application in supporting caregiving. Participants will also be shown and have the opportunity to work with examples of existing parenting/caregiving applications and will be asked to provide feedback on the usefulness of these existing applications.

Aim 2: Two-arm prospective, longitudinal, randomized 6-month pilot intervention. Recruited caregivers/infants will undergo simple randomization to one of 2 arms. The control arm (n=20) will receive printed caregiving materials based on recommendations outlined in Table 2. The intervention group (n=20) will receive the

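### Aim 2 pilot: the adjusted BSID4 comparison omits the enrolment BSID4 score already scheduled for every infant

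*Combined protocol and SAP*

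**What the plan says.** **Measurement.** The Study Protocol (Trial design and participants) states: "BSID4 data was collected at enrollment and study exit at 6 months post enrollment". The Protocol Summary Form (Study Procedures, Aim 2) agrees: "The BSID-4 will be measured at enrollment and study conclusion during a separate assessment visit". Neither limits the enrolment test to one arm.

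**Analysis.** The Statistical Analysis Plan says that "raw differences between intervention and control arms in composite scores were summarized and adjusted differences calculated using linear regression". The adjustment set, described as chosen *a priori*, is "sex of child, caregiver educational level, poverty score, birth weight and change in length for age Z score from 0 to 6 months". No change score, repeated-measures model or adjustment for enrolment BSID4 is described.

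**Outcome visit.** The analysis sentence names none. Table 1 says of Aim 2: "Outcomes assessed at 6 months". The Specific Aims say that "the developmental outcome (BSID-4) will be measured at 18 months in Aim 3 instead of 6 months in Aim 2".

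**Design and purpose.** Aim 2 has 20 dyads per arm: "Recruited caregivers/infants will undergo simple randomization to one of 2 arms". One stated purpose is to "determine effect size of clinical effectiveness (infant development outcomes").

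**The concern.** A baseline value of the outcome, on the same instrument, is an obvious candidate for adjustment in a randomised comparison, and here it is already scheduled. The plan adjusts for birth weight and social variables but not for the one direct measure of each infant's developmental starting point.

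Unbiasedness is not at stake: randomisation protects the comparison on average, and the standard error already allows for chance imbalance. Two things are at stake. The interval around the BSID4 difference may be wider than necessary. And with 20 per arm under simple randomisation, the single estimate obtained moves with whatever enrolment difference occurred, to the extent that enrolment predicts exit. Both matter because estimating an effect size is a stated aim of the pilot.

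**Working it through.** The plan gives no SD, power, interval or enrolment-to-exit correlation for BSID4, so there is no figure of its own to reproduce. What can be calculated is the effect of adding one covariate.

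**Inputs from the documents:** N = 40, 20 per arm (Table 1); q = 5 listed covariates, each counted as one term (Statistical Analysis Plan).

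**Assumed:** r, the partial correlation of enrolment with 6-month BSID4 given the five covariates, over 0 to 0.5. Results are in units of the residual SD of the 6-month composite given those covariates. The 95% interval is illustrative.

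**Without the enrolment score.** The variance of the difference before adjustment is 1/20 + 1/20 = 0.1. Adjusting for five covariates inflates it on average by (N − 3)/(N − q − 3) = 37/32. SE = √(0.1 × 37/32) = 0.340. With t(33 df) = 2.035, the half-width is 2.035 × 0.340 = 0.692.

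**With the enrolment score.** The inflation becomes 37/31 and the residual variance is multiplied by (1 − r²), so the variance ratio against the listed model is (1 − r²) × 32/31.

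| Assumed r | Variance ratio | SE | Half-width (t, 32 df) | Shift from a 0.5 SD imbalance (r × 0.5) |
|---|---|---|---|---|
| 0 | 1.032 | 0.345 | 0.704 | 0 |
| 0.2 | 0.991 | 0.338 | 0.689 | 0.10 |
| 0.3 | 0.939 | 0.330 | 0.671 | 0.15 |
| 0.5 | 0.774 | 0.299 | 0.609 | 0.25 |

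The last column is how far the difference moves if the enrolment score is left out and such an imbalance occurs.

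**Break-even.** (1 − r²) × 32/31 = 1 gives r = √(1/32) = 0.177. If education takes two terms, it is √(1/31) = 0.180. If only 36 or 32 infants are analysed (assumed), it is √(1/28) = 0.189 or √(1/24) = 0.204.

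**Simulation check.** With 20,000 simulated trials of 20 per arm and five other covariates, the variance ratios were 1.034, 0.991, 0.946 and 0.777. With coin-toss allocation they were 1.029, 0.992, 0.945 and 0.773. Both sets agree with the formula.

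**How often imbalance occurs.** For one composite, a raw difference in arm means of at least 0.5 SD has probability 2 × (1 − Φ(0.5/0.316)) = 0.114. After the five covariates it is 2 × (1 − Φ(0.5/0.340)) = 0.141. The second figure is in residual SD units, which equal raw SD units only if the covariates are unrelated to the enrolment score. It does not mean that adjustment worsens balance.

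**Missing enrolment scores.** If 10% are missing and mean-filled (assumed), the ratio is (1 − 0.9r²) × 32/31 = 0.949 at r = 0.3 and 0.800 at r = 0.5.

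**The case against.** The strongest case is that no defect has been shown. There is no bias, r is unknown, and the one relevant fact in the documents, testing at 0-28 days, may mean a low r. From r = 0 to 0.3 the half-width only moves from 0.69 to between 0.70 and 0.67 SD, and below about 0.18 the extra covariate loses precision. This stands as a limit on the size of the gain. It does not remove the asymmetry: the worst case widens the interval by about 2% (0.704/0.692), while r = 0.5 narrows it by about 12% (0.609/0.692).

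Second, the covariates were fixed *a priori* and the plan is written in the past tense, so an addition now may be post hoc. That stands, and it is why a completed analysis calls only for a labelled sensitivity model.

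Third, the outcome visit is inferred. A change-score reading is loosely possible, and the enrolment score would then already be in use. The text points the other way: the Aim 2 outcome is placed at 6 months, and the analysis sentence speaks of change only for length-for-age Z.

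Fourth, nothing says that the enrolment test preceded allocation. This is a real gap. Setting late scores to missing could also create missingness that differs by arm, which the 10% calculation does not cover. The remedy must therefore show results both ways.

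Finally, Table 1 calls BSID-4 primary for Aim 2 while Trial design and participants calls it secondary, and Aim 3 is already set at 110 per group. No claim is made that this change would alter that number.

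**Conclusion.** The concern holds, as an improvement to consider rather than an error that invalidates the analysis. The enrolment score is scheduled in both arms and absent from the adjusted model, and the plan gives no reason.

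The effect on variance runs from a 3% loss at r = 0 to a 23% reduction at r = 0.5, with break-even near r = 0.18. These figures assume 40 analysed infants, one term per covariate and an r that the documents do not supply; the true gain may be small or nil. The conclusion also rests on the 6-month composite being the outcome and on the enrolment test being a genuine pre-allocation baseline. It does not extend to Aim 3, for which the procedures schedule BSID-4 at 18 months and no enrolment test.

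**What to change.** - Name the 6-month composite as the outcome for each BSID4 domain, and add the same-domain enrolment composite to the regression. Leave the five listed covariates as they are; whether change in length-for-age Z should stay is a separate question.
- If the analysis has been run, keep the listed model and report this one beside it as a labelled sensitivity analysis.
- Fill missing enrolment scores with the pooled mean so that no infant is lost.
- Confirm that the enrolment test preceded allocation. If some tests followed handover of the app or printed materials, report the number by arm, treat those scores as missing in this model, and show the result both ways.
- Report the observed enrolment-to-exit correlation for each domain.
- State whether BSID4 is primary or secondary for Aim 2.

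The cost is one phrase naming the visit, one covariate, and a rule for missing or late scores, with no new data collection. If the enrolment score predicts nothing, the price is about 3% in variance (half-width 0.70 instead of 0.69 SD). A model added after the analysis has been run carries a post hoc label.
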